9.7	Data Analyses.....	73
10.	DATA COLLECTION AND QUALITY ASSURANCE	76
10.1	Data Collection Forms	76
10.2	Data Management.....	76
10.3	Quality Assurance.....	78
10.3.1	Training	78
10.3.2	Quality Control Committee	78
10.3.3	Metrics.....	78
10.3.4	Protocol Deviations.....	79
10.3.5	Monitoring.....	80
11.	PARTICIPANT RIGHTS AND CONFIDENTIALITY	82
11.1	Institutional Review Board (IRB) Review.....	82
11.2	Informed Consent Forms	82
11.3	Participant Confidentiality	82

11.4 Study Discontinuation.....	83
12. COMMITTEES.....	84
13. PUBLICATION OF RESEARCH FINDINGS	85
14. REFERENCES.....	78
15. SUPPLEMENTAL MATERIAL.....	89
I. Stanford IRB-Approved Informed Consent Form	
II. TMS Stimulation Manual	
III. TMS Blinding Manual	
IV. Hypnosis and Hypnotic Analgesia Manual	

STUDY TEAM ROSTER

[name]., Principal Investigator

[REDACTED]
[REDACTED]
Stanford, CA 94305
[contact]
Fax: [REDACTED]
Email: [contact]

[name]., Principal Investigator

[REDACTED]
[REDACTED]
Stanford, CA 94305
[contact]
Fax: [REDACTED]
Email: [contact]

[name]., Co-Investigator

[REDACTED]
[REDACTED]
Palo Alto, CA 94305
Phone: [REDACTED]
Fax: N/A
Email: [REDACTED]

[name]., Co-Investigator

[REDACTED]
Stanford, CA 94305 [REDACTED]
Phone: [REDACTED]
Fax: [REDACTED]
Email: [REDACTED]

[name]., Co-Investigator

[REDACTED]
[REDACTED]
Stanford, CA 94305 [REDACTED]
Phone: [REDACTED]
Fax: [REDACTED]
Email: [REDACTED]

PARTICIPATING STUDY SITES

[name]. Principal Investigator

Stanford University
Department of Psychiatry

██████████

██████████

Stanford, CA 94305

[contact]

Fax: ██████████

Email: [contact]

[name]. Principal Investigator

Stanford University
Department of Psychiatry

██████████

Stanford, CA 94305

[contact]

Fax: ██████████

Email: [contact]

PRÉCIS

Title

Use of Repetitive Transcranial Magnetic Stimulation (rTMS) to Augment Hypnotic Analgesia

Objectives

Primary Mechanistic Objective: To determine the effect of active, inhibitory rTMS (continuous theta-burst stimulation-cTBS) over left dorsolateral prefrontal cortex (L-DLPFC) on modulating the neural network that underlies hypnotizability and hypnosis.

Relevant Clinical Objective: To determine the effect of active, inhibitory rTMS (cTBS) over L-DLPFC on enhancing hypnotic analgesia (HA) as measured by change in pain thresholds.

Secondary Objective A: *To determine the effect of active, inhibitory rTMS (cTBS) over L-DLPFC on modulating the neural network that underlies hypnotic intensity.*

Secondary Objective B: *To determine the effect of active, inhibitory rTMS (cTBS) over L-DLPFC on enhancing hypnotizability (as measured by the Hypnotic Induction Profile-HIP and Stroop Task) and hypnotic intensity (as measured by the Hypnotic Intensity Scale-HIS).*

Secondary Objective C: *To determine the effect of active, inhibitory rTMS (cTBS) over L-DLPFC on the neural network underlying the conflict regulation system as a surrogate of effective modulation of the neural circuitry that underlies hypnotizability.*

Secondary Objective D: *To determine the effect of active, inhibitory rTMS (cTBS) over L-DLPFC on the neural network that underlies the post-hypnotic Stroop Effect.*

Secondary Objective E: *To determine the effect of active, inhibitory rTMS (cTBS) over L-DLPFC on modulating the neural network that underlies hypnotic analgesia (HA).*

[figure not shown]
Design and Outcomes

Study Design: This study is a double blind, placebo-controlled, mechanistic trial assessing rTMS as a strategy for the modulation of the neural circuitry underlying hypnotizability and hypnotic analgesia in participants with a diagnosis of Fibromyalgia Syndrome (FMS).

Schedule and Type of Evaluations: There are four visits for this. The first visit is a screening visit where the participant will be consented to be screened for the study. The participant will then be screened to determine inclusion and exclusion criteria. If the participant meets criteria, the participant will be consented for the imaging and rTMS portions of the study. The participant will be assigned their randomization code and their counterbalanced imaging days. Up to three separate imaging visits will be conducted including a baseline MRI for TMS target identification (Visit #2) and two separate MRI-TMS sessions consisting of a hypnotic analgesia and hypnotic stroop procedures (Visits #3-4). Visit #2 and #3 can take place on the same day. During the TMS-

MRI visits which include thermal pain and stroop MRI sessions, the participant will receive either sham or active rTMS (depending on randomization) in a non-crossover design.

Study Overview Diagram:

All participants will undergo the ***Hypnotic Stroop Scan Session Day***. All participants will receive the identical pre-rTMS scan session. One-half (n=50) will receive active rTMS and one-half (n=50) will receive sham rTMS (two arm, double-blind, sham-controlled). All participants will receive the identical post-rTMS scan session. Changes in resting state *functional connectivity* between L-DLPFC and dACC in the active rTMS versus the sham rTMS conditions will be assessed. This primary endpoint is a between-group comparison. We will also measure the difference in brain *activation* during the hypnotic induction, and Stroop task (after post-hypnotic suggestion) between the active and sham rTMS. This will also be a between-groups comparison. Using the *Hypnotic Induction Profile (HIP)* and *Hypnotic Intensity Scale (HIS)*, we will compare the change in hypnotizability and hypnotic intensity score between the active and sham rTMS groups.

All participants will undergo the ***Hypnotic Analgesia Scan Session Day***. All participants will complete identical pre- and post- rTMS scan session. One-half will receive active rTMS and one-half will receive sham rTMS. Changes in resting state *functional connectivity* between L-DLPFC and dACC in the active rTMS versus the sham rTMS conditions will be assessed. This primary endpoint is a between-group comparison. This scan-session also addresses a secondary aim of determining the difference in functional connectivity within the hypnotic analgesia network between the active and the sham rTMS groups. This will be a between-groups comparison. We will also compare the activation within the hypnotic analgesia network between the active and sham rTMS groups. This will be a between-groups comparison. We will also utilize a perturbation technique to probe the hypnotic induction in an alternative way. Finally, we will compare the difference in pain thresholds between the active and sham rTMS groups.

Interventions and Duration

Intervention: We will compare active versus sham rTMS as a technique for modulating the neural

circuitry underlying hypnotizability (Primary Mechanistic Outcome) in an effort to improve efficacy of hypnotic analgesia (Relevant Clinical Outcome). The total length of time that the participants will be four study visits. The study will involve one screening visit, three required scan session days (five required scan sessions including target identification scan, two pre-rTMS scan sessions, and two post-rTMS scan sessions).

Sample Size and Population

The target population is 18-70 year-old male and female participants who are low-moderately hypnotizable, have a confirmed diagnosis of fibromyalgia and have no contraindications to MRI or rTMS. We will enroll 100 pain medication-free (not taking opiates or anti-depressants on the day of rTMS) participants and employ a two-arm design with 50 subjects per arm.

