4.3 Study Enrollment Procedures

This study will recruit 100 individuals assuming about 20% missing data due to unusable imaging data and dropouts as has been previously demonstrated (34). The ability to be hypnotized is a stable and measurable trait that can be pre-screened and quantified (94, 105, 106). A member of the study team that has been trained by [name] will select subjects prior to randomization according to their ability to be hypnotized prior to the MRI visits using the Hypnotic Induction Profile (HIP). Hypnotizability is correlated about 0.6 with the ability to experience hypnotic pain relief (107). Participants will be selected those with low-moderate hypnotizability (scores of 0-8 on the HIP from a range 0-10) (94) in order to prevent a ceiling effect (see Appendix IV for the manual describing the HIP). IRB approval has been obtained to request that treating doctors at Stanford Hospital and Clinics send an invitation to patients they are seeing with Fibromyalgia Syndrome to participate in the study. Recruitment efforts will concentrate on physicians at the Stanford Center for Integrative Medicine, the Stanford Pain Clinic, the Stanford General Neurology Clinic, the Stanford Immunology and Rheumatology Clinic and the Stanford Chronic Fatigue Clinic.

The *NCCIH Site Screening and Enrollment Log* will be utilized to record the consent and screening of all subjects and the outcome of each screening. This log will provide a comprehensive list of all subjects who were screened for eligibility if the information is not maintained electronically. Subjects will be recorded as they are consented, to ensure completeness and accuracy of the data. All subjects will be included who were consented and screened, including screen failures. This log will not contain identifying information. Subjects will be tracked separately on logs in a coded list with a key. Each page will be numbered and maintained in this log in the *Essential Documents Binder*, behind the *Screening/Enrollment Log* tab. Pages will be stored in reverse chronological order, with the newest pages of the log placed at the front of the section. At the conclusion of the study, the final page of the log will be identified by checking the box in the footer.

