9.2 Sample Size and Randomization

For the power estimation, this study will use the significance level of .05 with two-tailed test. This study will recruit 100 individuals assuming about 20% missing data due to unusable imaging data and dropouts. In the Primary Mechanistic Hypothesis (formerly connectivity portion of Hypothesis 1a), power was estimated by focusing on the functional connectivity between DLPFC and dACC as the Primary Mechanistic Outcome. According to one prior study (47), the change in connectivity between DLPFC and dACC from pre to post rTMS is change in the quite large ($d=0.69$). We have augmented this one finding with numerous findings from other rTMS connectivity and functional activity studies, which demonstrated quite large effect sizes (see table 3 and table 4 below). Therefore, a somewhat conservative effect size of $d=0.8$ is being utilized for this study. The change from baseline to post-stimulation will be negligible in the sham rTMS group. Given this scenario, with the usable sample of 80 (40 rTMS, 40 sham), the estimated power is 0.8 ($\alpha=.05$, two-sided). For the Relevant Clinical Hypothesis (formerly Hypothesis 2b) and Secondary Hypotheses E (formerly Hypothesis 2a) as well as Secondary Hypotheses A, C, and D, both effect sizes and p-values will be monitored, with more emphasis on gathering information on effect sizes.

Manuscript	Site of Stimulation	Functional Connectivity Pair	Effect Size
Eldaief et al	L Posterior Intraparietal Lobule	rpIPL<->mPFC	0.72
Eldaief et al	L Posterior Intraparietal Lobule	rpIPL<->PCC	0.62
Nettekoven	Primary motor cortex	Primary Motor Cortex<->Premotor Cortex	0.9
Halko et al	Lateral cerebellum	DMN<->Posterior cingulate	1.26
Valchev et al	Primary somatosensory	Premotor	0.79

Vercammen Watanabe et al	Temporal-Parietal-Junction	Temporal-Parietal-Junction<->Right Insula	1.33
Watanabe et al	Left Motor Cortex	Left Motor Cortex<-> Right Motor Cortex	1.79
Watanabe et al	Left Motor Cortex	Left Motor Cortex<-> Right Motor Cortex	2

Table 3: Effect sizes for rTMS induced changes in functional connectivity as a surrogate for hypnotizability (Hoeft 2012)(31) modulated by rTMS(54, 56, 57, 158-160).

Manuscript	Stimulation Site	MRI/PET	Effect Size
Hubl	Frontal Eye Field	BOLD	0.4242
Bestmann	Motor/Somatosensory cortex	BOLD	2.36686405
Bestmann	Motor/Somatosensory cortex	BOLD	2.30589176
Cho	Right Dorsolateral prefrontal cortex	PET (CBF)	1.70333333

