This aim explores if active rTMS + HA will have produce greater anti-nociceptive effects on pain thresholds than sham rTMS. Inhibitory rTMS (cTBS) will be applied to L-DLPFC and it is expected that the stimulation-induced augmentation of hypnotic analgesia will be greater in the active rTMS condition over the sham rTMS condition. It is expected that the strength of this correlation will be greater than in the active rTMS + HA condition versus sham rTMS + HA given that the hypothesis is that the rTMS will increase fc between L-DLPFC and dACC which is believed to transiently modulate these participants to have similar response to hypnotic analgesia as do high hypnotizables(31) given the 0.6 correlation between measured hypnotizability and the ability to achieve hypnotic analgesia. HA network activation/connectivity to painful thermal stimulation will be assessed at baseline, during pre-rTMS hypnotic analgesia, after rTMS, and during post-rTMS HA. Changes in mean pain ratings between baseline pain and active rTMS + HA (TBS) and sham rTMS + HA conditions will be compared using ANOVA. It is expected that there will be a significantly greater mean decrease in pain ratings with the active rTMS + HA than the sham rTMS + HA condition at the $p < 0.05$, level.

Relevant Clinical Hypothesis: *Active, inhibitory rTMS over DLPFC will enhance hypnotic analgesia as compared to sham rTMS.*

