9.7 Data Analyses

The Primary Mechanistic Outcome Measure for this study is increased functional connectivity between the L-DLPFC and dACC. The Relevant Clinical Outcome Measure is change in hypnotic analgesia as measured by change in pain thresholds. For secondary aims, the emphasis is on identifying the magnitude of effects (clinical significance, effect size) instead of statistical significance. We will test whether the change in connectivity from baseline to post-treatment is greater in the active rTMS group as compared to the sham group. Following the convention in imaging studies, we will conduct our primary analyses treating the contrast (baseline versus post) as one univariate outcome. We do not expect much variation across our narrowly defined subjects, although some variation is still possible. Given that, we will also analyze the data in the linear mixed effects modeling framework (165, 166) allowing for random intercepts (although this is not customary in imaging studies) as a way of sensitivity analysis. The same analytical strategy will be used to test the effect of rTMS on the DLPFC and dACC activity, which is Secondary

Hypothesis A (previously activity portion of Hypothesis 1a-in grant), activity during conflict task (Secondary Hypothesis C), and during post-hypnotic instruction conflict task (Secondary Hypothesis D).

We are using thermal pain stimuli percept-matched to the individual receiving the intervention. Examining the treatment-effect moderating the role of the pain level is not a primary aim of this project.

Moderator/mediator investigation: We will explore various baseline variables as potential moderators of rTMS effect. For this investigation, we will employ the McArthur approach (167, 168) for moderator analysis. We will also examine potential mediators of rTMS effect using the McArthur approach (167, 168) as well as contemporary causal mediation approaches (169-174), which we believe will provide valuable insights regarding the neuromodulation mechanism for the next phase of investigation.

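### The hypnotic-analgesia comparison omits baseline hypnotizability, a covariate already collected; adjusting for it could cut the standard error by roughly 0 to 20%, depending on how the outcome is defined

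*Combined protocol and SAP*

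**What the plan says.** The précis describes the clinical comparison on the analgesia scan day in one sentence: "Finally, we will compare the difference in pain thresholds between the active and sham rTMS groups". The analyses are in Section 9.6.1 under the Relevant Clinical Outcome and Hypothesis. For change in mean pain ratings from baseline pain, the active and "sham rTMS + HA conditions will be compared using ANOVA". For the temperatures that evoke threshold and moderate pain, a linear mixed model is planned. No covariate is named for either.

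The rest of the plan does not supply one:

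- The general linear model in Section 9.2 has an intercept, a treatment indicator and an error term. Its mixed-model sensitivity version adds time and a random intercept.
- Section 9.7 adds scan-session order, and otherwise uses unnamed baseline variables only in exploratory moderator work.
- Age, sex and time between visits are regressors only in the spectroscopy analysis (Section 9.6.2, Outcome F).
- Randomization is by permuted block with no hypnotizability stratum named (Sections 6.2.2 and 9.3).
- The separate SAP gives rank tests of HIP change and no pain analysis.

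On the covariate itself, Section 4.3 says: "Hypnotizability is correlated about 0.6 with the ability to experience hypnotic pain relief (107" (the closing number is a literature reference). Section 9.6.1 repeats the 0.6 within the clinical outcome. Section 4.1 admits HIP scores of 0 to 8, on a scale that Section 4.3 gives as 0 to 10. Section 6.2.1 has HIP administered twice at the screening visit.

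**The concern.** The protocol identifies a strong predictor of the response it wants to measure, keeps most of that predictor's range in the trial, records it before stimulation, and then leaves it in the error term. Section 9.2 states no power for the clinical hypothesis and stresses effect-size information instead, so the width of the confidence interval is what counts for this outcome. If hypnotizability explains much of the between-person variation in pain change, the unadjusted interval is wider than it needs to be, although no further data would be required to narrow it.

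For the rating analysis there is a supporting argument. Section 9.7 states: "We are using thermal pain stimuli percept-matched to the individual receiving the intervention". Baseline ratings are therefore similar by design, and a baseline rating can explain little. This does not carry over to the threshold endpoint: matching equalises perceived intensity, not temperature, and baseline threshold temperature may itself be a useful covariate there.

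**Working it through.** **The plan's own figure.** The only stated power is for the connectivity outcome: "a somewhat conservative effect size of $d=0.8$ is being utilized for this study", and "with the usable sample of 80 (40 rTMS, 40 sham), the estimated power is 0.8". A two-sample t test with d = 0.8, 40 per arm and two-sided 0.05 gives power 0.942, not 0.8; d = 0.69, from the one study cited for this connection, gives 0.862. Power of 0.8 at 40 per arm corresponds to d = 0.634. The loss allowance does reproduce: 80/(1 − 0.2) = 100. The power discrepancy is a separate matter, and there is no clinical power figure to reproduce. Only the sample of 80 and the two-sided 0.05 level are used below.

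**Inputs.** N = 80, 40 per arm (Section 9.2). Correlation r = 0.6 (Sections 4.3 and 9.6.1). HIP range 0–8 out of 0–10 (Sections 4.1 and 4.3). Assumptions not in the documents: uniform HIP scores for the range-restriction step, and an illustrative effect of 0.5 SD for the power column.

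**Step 1: restricted range.** With uniform scores the SD ratio is u = 8/10 = 0.8. Then r′ = ru/√(1 − r² + r²u²) = 0.48/√(0.64 + 0.2304) = 0.48/0.933 = 0.514.

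**Step 2: gain from adjustment.** Adjusted over unadjusted variance = (1 − r²) × [1 + 1/(N − 4)], where the bracket, 1 + 1/76 = 1.013, is the price of estimating the slope. For r = 0.6: 0.64 × 1.013 = 0.648, square root 0.805, equivalent sample 80/0.648 = 123. The detectable difference at 80% power is 0.634 times the SE ratio.

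| r | Variance ratio | SE ratio | Equivalent N | Detectable d | Power at 0.5 SD |
|---|---|---|---|---|---|
| unadjusted | 1 | 1 | 80 | 0.634 | 0.60 |
| 0.6 | 0.648 | 0.805 | 123 | 0.511 | 0.78 |
| 0.514 | 0.745 | 0.863 | 107 | 0.548 | 0.73 |
| 0.3 | 0.922 | 0.960 | 87 | 0.609 | 0.63 |
| 0 | 1.013 | 1.007 | 79 | 0.638 | 0.59 |

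Break-even: (1 − r²) × 1.013 = 1 gives |r| of about 0.11.

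**Step 3: simulation check.** With 8,000 trials per scenario and HIP uniform on 0–8, the SE ratios were 0.802, 0.858, 0.962 and 1.007 for r = 0.6, 0.514, 0.3 and 0, in agreement with the formula. With r = 0.6 under sham and 0.3 under active the ratio was 0.902; with 0.6 under sham and 0 under active it was 0.958.

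**Step 4: which change is analysed.** Section 9.6.1 contrasts pre-stimulation pain with stimulation plus hypnotic analgesia. The baseline threshold step in Section 6.2.2 mentions no hypnosis. On that reading the change contains the whole hypnotic response, and the trait stays in it. Section 9.7, however, names the outcome as change in hypnotic analgesia, and Sections 6.2.2 and 9.6.1 also provide for analgesia under hypnosis before stimulation. In a hypnosis-to-hypnosis contrast a stable trait enters both terms and largely cancels, so r approaches 0 and so does the gain.

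**The case against.** The strongest reply is that the size of the gain is not established. The 0.6 relates to the ability to obtain hypnotic pain relief; the documents do not say that it was measured with the HIP or that it holds for change in threshold. The trial's own hypothesis works against it too: if active stimulation makes low-to-moderate participants respond like high hypnotizables, baseline HIP should predict less in that arm, and the saving falls to about 4% if the link survives only under sham. All of this stands, and it is why the gain has to be given as a range.

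A reader might infer that adjustment is worth a 36% cut in variance, or 1.56 times the participants. Those figures need r = 0.6 to apply in full to the analysed outcome in both arms, which the documents do not show. A reader might also infer that the unadjusted comparison is biased. It is not: assignment is randomized.

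Forty per arm may also be too few for thresholds. The 20% loss in Section 9.2 covers unusable images as well as dropout, while Section 6.2.2 measures thresholds outside the scanner. At 50 per arm, unadjusted power at 0.5 SD is about 0.70 rather than 0.60. The proportional SE saving barely moves, since the bracket becomes 1 + 1/96.

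Finally, Section 9.2 deliberately chooses a simple arm comparison, and the SAP is dated January 2024 and written in the past tense. Making an adjusted estimate the main result now would change the estimator after data collection. That objection stands against an unlabelled switch, not against the adjustment itself.

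**Conclusion.** The omission is confirmed, and adjusting is the better choice. The likely SE reduction is roughly 0 to 20%: about 20% if r = 0.6 applies, 14% at 0.51 (uniform scores assumed), 4% at 0.3 or if the link holds only under sham, and near zero if the pre-stimulation measure is also under hypnosis. The downside is an SE increase of about 0.7% at r = 0, and adjustment pays whenever |r| exceeds about 0.11. The power figures at 0.5 SD and 40 per arm are illustrations, not statements about this trial. This is an inexpensive gain in precision on an outcome where the plan stresses effect size; it does not threaten the validity of the comparison. The percept-matching argument supports it for pain ratings only.

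**What to change.** In Section 9.6.1, name one pre-randomization HIP score, for example the mean of the two screening administrations, as a covariate in both the pain-rating ANOVA and the mixed model for temperatures. Report the adjusted and unadjusted active-minus-sham differences with 95% confidence intervals side by side.

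Two details should be written down. First, use the screening score and not a scan-day one: session order is counterbalanced, so HIP taken before stimulation on a second scan day follows an earlier stimulation. Second, if the mixed model takes pre- and post-stimulation temperatures as repeated outcomes, HIP should enter with its interaction with time; a main effect alone shifts the level, which the random intercept already absorbs, and leaves the change untouched. The same passage should state whether the pre-stimulation pain measure is taken with or without hypnosis, since the value of the adjustment depends on it.

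The cost is a sentence or two in Section 9.6.1, no new data, and one degree of freedom in the ANOVA (slightly more in a mixed model with the interaction). The SAP would need a pain analysis before a covariate could be added to it. If the adjustment is adopted now, label it as added after data collection, with the protocol's own 0.6 as the rationale that predates the analysis, and keep the unadjusted result in view.
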